#### **8.1.3.4. Colonization with *Staphylococcus aureus***

Colonization values obtained up to 7 days before vaccination until the day of admission for surgery will be considered eligible baseline values.

Colonization at each visit, acquisition, and clearance are binary endpoints, so they will be summarized with proportions. Vaccine groups will be compared using the CMH test. Site will be the stratification variable.

Carriage status will form a  $3 \times 2$  table with 3 categories—“persistent,” “intermittent,” and “noncarrier”—and 2 vaccine groups. “Indeterminate” will be considered a missing value. Vaccine groups will be compared using the CMH test. Site will be the stratification variable.

Subgroup analyses will be performed by executing logistic regressions with the dependent variable of the proportion of subjects colonized. The model terms will be vaccine group, subgroup, and vaccine group–subgroup interaction. The colonization results for subgroups with significant interactions, defined as  $p < 0.10$ , will be examined more closely.

One subgroup will be examined at a time. Anatomical sites will be examined separately. Only colonization at scheduled visits will be included. Only *S aureus* colonization will be analyzed because the purpose is to see if vaccine group has different effects within subgroup levels.

Vaccine groups will be compared using the Fisher exact test, 2-sided, for the proportion positive for *S aureus* from unscheduled visits. Stratification by clinical site is not proposed because the unscheduled visits will presumably be associated with possible BSI/SSI/ISA.

The number of these assessments per site should be low. Analyses will be performed by anatomical site and for anatomical sites combined.

Isolates from microbiologically confirmed cases: The association between the *S aureus* strain or strains identified as colonizing the subject and the *S aureus* strain or strains recovered from the PDI will be examined for subjects with microbiologically confirmed *S aureus* infection. Strains will be identified using whole-genome sequencing (WGS). These strains will be paired with the strain or strains from the previous scheduled visit and from the day-of-surgery visit. Matches will be scored as “yes” or “no.” If there is no colonization result, then the match will be scored as “missing.” The strain identified as colonizing the subject will be obtained from the unscheduled visit associated with the microbiologically confirmed infection. The infection-colonization match will be “yes” if the strain from the microbiologically confirmed case matches the strain from either anatomical site”; otherwise, it will be “no.” Vaccine groups will be compared using the Fisher exact test, 2-sided. Comparisons will be performed separately for matches to the day of surgery and matches to a previous scheduled visit.

Colonization at unscheduled visits: Nose and throat swabs will be collected at unscheduled visits for BSI/SSI assessment. The proportions of subjects with at least 1 positive swab at any unscheduled visit will be compiled for each vaccine group. The proportions will be compiled for nose, throat, and any anatomical site. In the latter case, a positive swab in either anatomical site is sufficient to declare a positive result. This will be performed for any *S aureus*, MRSA, and MSSA. The denominators will be the number of subjects with any swabs at any unscheduled visit. Vaccine groups will be compared using the Fisher exact test, 2-sided.

Statistical analyses for colonization are summarized in [Section 8.2.3.4](#).

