- g. Serum or capillary; fasting value required preoperatively.
- h. Physical examination includes general appearance; musculoskeletal; skin; head, eyes, ears, nose, and throat; heart; lungs; abdominal; neurological; and lymph nodes.
- i. Only applicable for women of childbearing potential. Pregnancy testing may be performed on urine or serum samples.
- j. Record the surgical indication and the planned index surgical procedure. Postoperatively, record the actual index surgical procedure.
- k. Immunogenicity blood draw and colonization swabs must be collected before vaccination at Visit 1 (window: 7 days) and before surgery at Visit 2.
- l. Refer to the respective study visit as detailed in [Section 6](#).
- m. Daily observation for PDIs, AEs, and organ failure events as detailed in [Section 6.3.1.2.1](#).
- n. The e-diary should be collected and AE data reviewed with the subject prior to surgery.
- o. Refer to Appendix 4.

SCHEDULE OF ACTIVITIES FOR ADVERSE AND STUDY EVENT REPORTING

The Schedule of Activities for Adverse and Study Event Reporting table provides an overview of the protocol safety reporting requirements. Refer to the Study Procedures ([Section 6.1](#)) and Assessments ([Section 7](#)) sections of the protocol for detailed information on each procedure and assessment required for compliance with the protocol.

Table 2. Schedule of Activities for Adverse and Study Event Reporting

Visit ID	1	2			3	4	5	6
Protocol Activity	Enrollment and Day of Vaccination	Index Hospital Admission			Day 21 Telephone Contact	Day 42 Postoperative Evaluation	Day 90 Postoperative Evaluation	Day 180 Postoperative Evaluation
		Day of Surgery	Day After Surgery	Day of Discharge				
Study Day	Day -60 to Day -10	Day 1	Day 2	(Day Variable)	Day 21	Day 42	Day 90	Day 180
Visit Window	Day -60 to Day -10	N/A	N/A	N/A	Day 18 to Day 26	Day 35 to Day 49	Day 83 to Day 97	Day 178 to Day 192
Local reactions and systemic events collected in the e-diary	From the day of vaccination for a total of 10 days ^a							
Adverse events	AEs from informed consent to the Day 42 postoperative evaluation							
						Newly diagnosed chronic medical disorders from the Day 42 postoperative evaluation to the Day 180 postoperative evaluation		
Serious adverse events	SAEs from informed consent to the Day 180 postoperative evaluation							
Protocol-defined infection events	PDI events from after surgery to the Day 180 postoperative evaluation							

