9.3.4.2. Colonization Analysis

Windows for obtaining colonization swabs will be the same as for immunogenicity. Colonization swabs at Visit 2 (index hospital admission) will be collected both on admission and again, prior to discharge.

Baseline colonization status is defined as:

- Positive for any subject with at least 1 positive *S aureus* colonization swab at either Visit 1 or Visit 2 (admission sample only) or both.
- Negative for any subject with all negative *S aureus* colonization swabs at both Visit 1 and Visit 2 (admission sample only) and no missing colonization swabs.
- Missing for subjects without any colonization swab results from either Visit 1 or Visit 2 (admission sample only) or subjects with any combination of negative colonization swabs and at least 1 missing colonization swab.

At each postsurgery time point, the proportions of colonization swabs testing positive for *S aureus* at each anatomical site and the RR between the 2 vaccine groups along with its exact 2-sided 95% CI will be obtained. Subgroup compilations will be performed based on

age group, sex, baseline colonization status, and primary endpoint status (ie, case or noncase). Statistical significance of treatment-subgroup interactions will be obtained from logistic regression. The logistic regression will include treatment, subgroup, and treatment-subgroup interaction. One subgroup will be examined at a time. Some subgroups may be combined to achieve reasonable sample size. Anatomical sites will be examined separately.

Analyses will be performed for the per-protocol and mITT populations, further limited to subjects having at least 1 nonmissing colonization swab value at any visit.

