**8.2.3.4. Colonization with *Staphylococcus aureus***

All analyses will be performed using the mITT colonization population.

The proportions of subjects with positive swabs will be plotted against time point. The time points' labels on the figures will be "Day of Vaccination," "Day of Surgery," "Day of Discharge," "Day 42," "Day 90," and "Day 180." The values for the time points will be -15, 1, 2, 42, 80, and 180. The legend will identify anatomical site (nasal/oropharyngeal/combined). Plots will be created for "any *S aureus*," MSSA, and MRSA.

Subgroup analyses will be performed on colonization, carriage status, acquisition, and clearance. The subgroups will be age group, sex, baseline colonization status, and primary endpoint (case or noncase). The subgroup analysis of the primary endpoint will be limited to scheduled visits within 90 days, as per definition of the primary endpoint.

A further subgroup will be defined by subjects having any decolonization measures or preadmission antimicrobial agent(s) before surgery (response = yes/no). These analyses will be performed only for "any *S aureus*."

The analysis of matching isolates from microbiologically confirmed cases will be performed separately for nose and throat for each of the efficacy endpoints (BSI and/or deep incisional or organ/space SSI within 90 days, BSI and/or deep incisional or organ/space SSI within 180 days, SSI within 90 days, SSI within 180 days, ISA disease within 90 days, and ISA disease within 180 days), but limited to subjects in the mITT colonization population. If there may be more than 48 cases for the primary endpoint, ie, with BSI and/or deep incisional or organ/space SSI, these extra cases will be included in this analysis.

Colonization analyses and their statistical tests are summarized in Table 25.

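### The per-visit colonization comparison is valid but leaves out the pre-vaccination swab, which gives up some precision, and the SAP does not restate the protocol's relative risk with 95% CI

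*SAP*

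**What the plan says.** - **Endpoint and test.** SAP 8.1.3.4: "Colonization at each visit, acquisition, and clearance are binary endpoints, so they will be summarized with proportions". It continues: "Vaccine groups will be compared using the CMH test. Site will be the stratification variable". SAP Table 25 repeats this for colonization on each visit, with site as the only stratification variable.
- **The pre-vaccination swab.** Protocol Table 1, footnote k: "Immunogenicity blood draw and colonization swabs must be collected before vaccination at Visit 1", with a 7-day window.
- **Effect estimate.** Protocol 9.3.4.2, for each postsurgery time point: "the RR between the 2 vaccine groups along with its exact 2-sided 95% CI will be obtained". SAP 8.1.3.4 and Table 25 do not mention a relative risk, or a confidence interval for the vaccine contrast.
- **Where earlier swabs are used.** SAP 8.2.3.4 on subgroups: "The subgroups will be age group, sex, baseline colonization status, and primary endpoint (case or noncase". SAP 8.1.3.4 on the logistic model for them: "The model terms will be vaccine group, subgroup, and vaccine group–subgroup interaction". Acquisition and clearance (SAP 6.3.4) are also defined by reference to earlier swabs.
- **What baseline means.** SAP 8.1.3.4: "Colonization values obtained up to 7 days before vaccination until the day of admission for surgery will be considered eligible baseline values". It can therefore include the Visit 2 admission swab, which is taken after vaccination.
- **Status.** Colonization is an exploratory objective with descriptive wording (protocol 2.4).

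**The concern.** A person's carriage before vaccination is likely to predict carriage at later visits. When a binary outcome has a strong baseline predictor, a comparison that leaves it out is less precise than the data allow. Here the predictor is collected by design. The SAP already uses Visit 1 colonization as a covariate in one immunogenicity ANCOVA (SAP 8.1.3.5, Visit 1 versus Visit 2 admission), but not where colonization is itself the outcome.

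The effect estimate is a related gap. Table 25 gives the purpose of several rows as exploring what vaccination does to carriage, acquisition and clearance. That calls for an effect size with an interval, not only two proportions and a test result.

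**Working it through.** **Figures in the plan.** The documents give no sample size, power or precision for colonization, so there is no figure on this point to reproduce. The planned N can be checked against protocol 9.2 (48 cases, placebo incidence 1.4%, 10% dropout):

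- VE 70%: 48 / (0.014 × (1 + 0.3)/2) = 5,275 evaluable; 5,275/0.9 = 5,862, against about 6,000 stated.
- VE 60%: 48 / (0.014 × (1 + 0.4)/2) = 4,898 evaluable; 4,898/0.9 = 5,443, against about 5,440 stated.

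The planned size is therefore a fair basis: 6,000 × 0.9 / 2 = 2,700 per arm. The actual number is lower and not given, because enrollment stopped at the interim analysis (SAP 8.1.3.5).

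**Inputs.** Carriage of 20% to 50% is the general background figure in protocol section 1; 35% is its midpoint. The correlation φ between the Visit 1 swab and a later swab is not in the documents and is assumed to be 0.2 to 0.7.

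**Formulas.** Unadjusted SE of the risk difference = √(2p(1−p)/n). At p = 0.35 and n = 2,700 this is √(0.455/2,700) = 1.30 percentage points, a 95% half-width of about 2.5 points (2.1 at 20% carriage, 2.7 at 50%). Adjusting for a binary baseline multiplies the variance by 1 − φ² and the SE by √(1 − φ²). Power is for 35% versus 32%, two-sided 5%, with n replaced by n/(1 − φ²).

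| Assumed φ | 1 − φ² | Variance falls by | SE falls by | SE (points) | Power |
|---|---|---|---|---|---|
| unadjusted | 1 | – | – | 1.30 | 65% |
| 0.2 | 0.96 | 4% | 2.0% | 1.27 | – |
| 0.3 | 0.91 | 9% | 4.6% | 1.24 | 69% |
| 0.5 | 0.75 | 25% | 13.4% | 1.12 | 77% |
| 0.6 | 0.64 | 36% | 20.0% | 1.04 | 83% |
| 0.7 | 0.51 | 49% | 28.6% | 0.93 | 91% |

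The proportional gain depends on φ, not on N, so the early stop does not change it.

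**Cross-check against the planned test.** A simulation compared CMH by site with CMH by site crossed with the Visit 1 swab. It used 5,400 subjects, 100 sites of equal expected size (assumed), a true difference of 3 points, and 1,000 runs at each of 20%, 35% and 50% carriage.

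- SE ratio, adjusted to planned: 0.95–0.97 at φ = 0.3, 0.86–0.90 at 0.5, 0.72–0.74 at 0.7.
- Power at 35% carriage: 66% to 68%, 65% to 77%, and 63% to 87% respectively.
- With no vaccine effect (35% carriage, φ = 0.6, 2,000 runs), both tests rejected in 5.0% of runs.

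**Do the other analyses fill the gap?** The subgroup logistic model takes one subgroup at a time, includes an interaction and has no site term. It gives effects within baseline levels, not one pooled estimate, and its baseline may include a post-vaccination swab. Acquisition also depends on the presurgery swab. The denominators for acquisition and clearance are subjects with any nonmissing swab, not those negative or positive at baseline. None of these gives an overall per-visit effect adjusted for the Visit 1 result.

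**The case against.** The strongest reply is that the planned comparison is an acceptable choice for a descriptive, exploratory aim. Randomization is 1:1, the test holds its level, and the objective drives no decision. Baseline colonization is tabulated by group and used as a subgroup, and acquisition and clearance condition on earlier swabs. Surgery up to 60 days after vaccination, decolonization measures, perioperative antibiotics and follow-up to Day 180 could all weaken the link between swabs, so the gain may be small. An adjusted analysis also has to deal with small sites and missing Visit 1 results. All of that stands, and it limits the size and priority of the point. It does not supply the adjusted overall estimate.

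A reader might infer four stronger things that the documents do not support:

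- **That the vaccine effect is estimated far less precisely than it could be, because the strongest predictor is left out.** The documents give no swab-to-swab correlation and do not rank predictors. A large loss appears only at the top of the assumed range.
- **That chance imbalance in carriage could be mistaken for a vaccine effect.** The type I error of the randomized comparison already allows for chance imbalance, and the simulation under no effect shows 5.0% rejection.
- **That baseline carriage is ignored.** It is used, but not in the overall per-visit comparison.
- **That the SAP withdraws the relative risk and leaves only a p-value.** Group proportions are reported and plotted, the relative risk remains in the protocol, and the SAP is silent on it rather than revoking it.

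**Conclusion.** The point holds as one of efficiency and reporting. The overall per-visit colonization test is valid but does not adjust for a pre-vaccination swab that is already collected and is likely to be a strong predictor. The cost ranges from almost nothing to material: about 2% to 29% of the standard error (4% to 49% of the variance) for assumed φ from 0.2 to 0.7. There is no bias and no inflation of type I error, and no trial decision rests on this endpoint. The missing relative risk and interval is a plain mismatch between protocol 9.3.4.2 and the SAP's colonization sections, and it needs no assumption about correlation.

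**What to change.** - For each post-vaccination visit, add a supportive analysis of colonization adjusted for Visit 1 colonization at the same anatomical site and for study site. Report the adjusted relative risk or risk difference with a 95% CI beside the planned CMH test.
- Use the Visit 1 swab only. The Visit 2 admission swab follows vaccination, so adjusting for it could remove part of any vaccine effect.
- State in advance how sparse sites will be pooled, and give a missing Visit 1 result its own category so that no subject is dropped.
- Carry the protocol's relative risk with exact 95% CI at each postsurgery time point into SAP 8.1.3.4 and Table 25.
- Leave acquisition and clearance as defined.

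The cost is some SAP wording and a small amount of extra analysis. No new data are needed.

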### **8.1.3.5. Immunogenicity**

On December 20, 2018, the STRIVE study met its pre-specified futility criteria at its Interim Analysis and ceased enrollment. The rationale for this change in immunogenicity testing and analysis is to focus efforts on improving our understanding of why the vaccine did not appear to prevent post-operative *S. aureus* infections. This analysis will replace all previously planned immunogenicity analyses.

The immunogenicity testing and analysis will focus on the four objectives listed below:

Primary objective:

1. To assess the association between CP5/8, ClfA, and MntC functional antibody levels and *S. aureus* infections among subjects within the STRIVE study, adjusting for demographics, health status, and surgical characteristics

Secondary objective:

2. To describe the CP5/8, ClfA, and MntC functional antibody levels among surgical subjects at selected time points by case and vaccination status

Exploratory objectives:

3. To compare the functional immune response to CP5/8, ClfA, and MntC among vaccinated surgical subjects without *S. aureus* infection with vaccinated healthy (non-surgical) subjects
4. To compare the functional immune response of CP5/8, ClfA, and MntC at unscheduled BSI/SSI visit among subjects with *S. aureus* infection with scheduled visits of similar time intervals among subjects without *S. aureus* infection

Study Design:

A nested case-control study within the STRIVE study will be conducted to assess the association of *S. aureus* infection and immunogenicity endpoints at select timepoints, adjusting for demographics, health status, and surgical characteristics. Cases and controls will be matched by study site.

Cases will be any subjects (per protocol or mITT) with adjudication-confirmed *S. aureus*-related SSI and/or BSI (includes deep, organ/space and superficial SSIs). Infections with positive *S. aureus* cultures deemed not clinically significant by adjudicators will be excluded. Other invasive *S. aureus* infections will have descriptive analysis separate from objective 1 and without matched controls. At this time, there are 5 such cases: additional cases may be identified prior to study closeout.

Controls will be per protocol subjects from same study site as cases who completed Visit 5 (post-op Day 90) but did not develop adjudication-confirmed *S. aureus* infections. A total of 7 controls will be selected per case (5 vaccinated and 2 unvaccinated controls per case).

At this time, the plan is to include a total of 51 cases of *S. aureus* infection (both SA4Ag vaccinated and placebo) and 357 controls will be included in this sub-analysis. For the few sites with a shortfall in available controls due to low enrollment, remaining controls will be randomly selected from other “case” sites (ie, sites with cases that have unselected controls remaining) to meet control targets. Extra controls will be associated with their actual site in the logistic regression analysis.

Data analysis:

All analyses will be performed for CP5/OPA, CP8/OPA, ClfA/cLIA, and MntC/cLIA.

*Objective 1:*

The key independent variables of interest are CP5 and CP8 functional antibody levels (as measured by OPA assay), and secondary independent variables include ClfA and MntC antibody levels (as measured by cLIA assay) assessed at the following time points.

The primary analysis will include the following immunogenicity variables (one value for each antigen for each specimen):

- Day of index surgery before surgery (V2 admission) log transformed titers
- V2 hospital discharge log transformed titers minus V2 admission log transformed titers [Quantify change from V2 admission]
- V5 post-op day 90 log transformed titers minus V2 hospital discharge log transformed titers [Quantify change from V2 discharge]

Multivariate conditional logistic regression will be conducted to model the odds of *S. aureus* infection based on functional antibody levels (ie, 3 immunogenicity variables based on V2 and V5 described above), adjusting for following covariates:

- Demographics (age, sex, race/ethnicity, BMI, ASA, CCI)
- Operative time (mins)
- Number of motion segments/intervertebral levels fused
- Proportion of blood loss (%)
- Units of transfusion
- Days from vaccination to surgery
- Days from surgery to discharge
- Primary versus revision spinal fusion surgery
- Season/year of surgery
- Colonization status (IHMA swab results)
- Diabetes
- Smoking status
- Intrawound antibiotic use (eg, vancomycin vs. other vs. none)

It is recognized that this is an extensive list of potential covariates with a limited sample size. Model selection will attempt forward or backward selection approaches to arrive at a parsimonious model. Results will be reported as odds ratios (ORs) with corresponding 2-sided 95% CIs. Effect modification/interaction will be tested for select variables (eg, vaccination status, colonization status, blood loss, units of transfusion). Results of the multivariable conditional logistical regression will be reported as odds ratios (ORs) with 95% confidence intervals (CIs). Frequency counts and summary statistics (n, mean, standard deviation, median, minimum, and maximum) will be compiled for serology results and all covariates listed above by case/control status.

Proportion of blood loss will be estimated from blood loss (ml) divided by the estimated preoperative blood volume. Estimation of preoperative blood volume depends on sex:

- Male: volume (mL) =  $(0.006012 \times H^3)/(14.6 \times W) + 604$
- Female: volume (mL) =  $(0.005835 \times H^3)/(15 \times W) + 183$
- where H = height in inches and W = weight in pounds.

Additional sensitivity analyses include 1) repeating overall model for STRIVE primary endpoints only, 2) excluding controls with other non-*S. aureus* infections, and 3) limiting analysis to per protocol subjects.

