### **5.1. Modified Intent-to-Treat Efficacy Populations**

To be included in the mITT efficacy population, a subject must be vaccinated and undergo spinal surgery. Subjects will be assigned to the investigational product to which they were randomized (SA4Ag or placebo).

Subjects who do not undergo spinal surgery following vaccination will not be included in the mITT efficacy population. If any efficacy data are collected in these subjects, it will be listed separately.

A subset of the mITT efficacy population, referred to as the restricted mITT efficacy population, will also exclude subjects with a pre-existing infection, or malignancy, or acute or emergency trauma, at any time from enrollment up to and including the time of the index surgery. This population will be used for selected efficacy analyses only (see [Section 8.2.1](#)).

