### 5.6.2. Protocol Deviations Occurring After Randomization

1. Vaccinated subjects who do not undergo the planned index surgery will be included only in the safety population.
2. Nonvaccinated subjects will be excluded from all populations.
3. Subjects will be excluded from the PP efficacy population for any of the following reasons:
  - a. Not vaccinated as randomized
  - b. Undergoing index surgery 8 days or sooner after vaccination *or* 91 days or later after vaccination
  - c. Not meeting 1 or more of the study-defined criteria for the index surgery
  - d. Having 1 or more major protocol deviations expected to affect efficacy or immunogenicity, prior to the onset date of suspected *S aureus* infection as determined by a medically qualified clinician at the sponsor
  - e. Suspected or confirmed infection or malignancy identified during the index surgical procedure

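### Objective 1 of the post-futility immunogenicity study takes cases from mITT subjects but controls only from per-protocol subjects, which can bias the antibody-infection odds ratio if protocol status is related to titer

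*SAP*

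**What the plan says.** SAP 8.1.3.5 replaces the earlier immunogenicity analyses after the futility stop. Its primary objective (Objective 1) is the association between functional antibody levels and *S. aureus* infection among trial subjects, estimated by conditional logistic regression with matching on site.

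- **Cases:** "Cases will be any subjects (per protocol or mITT) with adjudication-confirmed" surgical-site or bloodstream infection due to *S. aureus*.
- **Controls:** "Controls will be per protocol subjects from same study site as cases who completed Visit 5 (post-op Day 90", and without confirmed *S. aureus* infection.
- **Ratio:** "A total of 7 controls will be selected per case (5 vaccinated and 2 unvaccinated controls per case".
- **Size:** the SAP plans for 51 infected subjects across both arms, "and 357 controls will be included in this sub-analysis".
- **mITT (SAP 5.1):** "To be included in the mITT efficacy population, a subject must be vaccinated and undergo spinal surgery". Eligibility and adherence play no part.
- **Per-protocol (SAP 5.2, 5.6.1, 5.6.2):** excludes ineligible subjects, subjects not vaccinated as randomized, surgery outside 9 to 90 days after vaccination, non-conforming surgery, major deviations judged likely to affect efficacy or immunogenicity, and "Suspected or confirmed infection or malignancy identified during the index surgical procedure".
- **Sensitivity analyses:** one of the three planned for Objective 1 is "limiting analysis to per protocol subjects". SAP Table 26 repeats it.

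Table 26 assigns the Objective 1 model to the mITT immunogenicity population (SAP 5.4.1), which carries no per-protocol restriction. The SAP gives no reason for drawing cases and controls from different populations.

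**The concern.** In a nested case-control study, controls should represent the population that produced the cases. Here the frequency of non-per-protocol subjects among controls is zero by design, while among cases it is whatever occurred. If non-per-protocol subjects have different titers, that difference enters the case-control contrast and can pass for an antibody effect, even when antibody has no effect and deviation does not change infection risk.

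A link between protocol status and titer is plausible from the documents. SAP 5.6.2 removes subjects for deviations expected to affect efficacy or immunogenicity. The eligibility criteria in protocol section 4.2 cover immunosuppressant treatment and recent blood products. Surgery 8 days or sooner after vaccination also leads to exclusion.

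The covariates do not close the gap. They include days from vaccination to surgery, which forward or backward selection may drop, but nothing for eligibility failure, type of deviation, misallocation or infection found at surgery. A per-protocol indicator could not be estimated in the planned design, because no control would be non-per-protocol.

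At stake is the primary objective of an analysis meant to explain why the vaccine did not appear to prevent infection. If non-per-protocol titers are lower, the shift is toward apparent protection by antibody. If they are higher, it is the other way.

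**Working it through.** **Plan's figure.** 51 × 7 = 357 controls (51 × 5 = 255 vaccinated and 51 × 2 = 102 unvaccinated). This reproduces. SAP Tables 12 and 13 also use 350 (50 × 7), a separate inconsistency with no bearing here.

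**Inputs the documents do not give (assumptions):**
- f: share of mITT subjects who are not per-protocol; 5%, 10% or 20%.
- d: titer of non-per-protocol minus per-protocol subjects; 0, −0.25, −0.5 or −1 SD.
- RR: infection risk of non-per-protocol relative to per-protocol subjects; 1 or 2.

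Titer is assumed to have no effect on infection within each protocol status.

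**Formulas.** The non-per-protocol share among cases is q = f·RR / (f·RR + 1 − f). Among controls it is c. With roughly normal titers of equal variance, the odds ratio per SD is about exp[d(q − c)]. As planned, c = 0. With mITT controls, c = f. With per-protocol cases and controls, q = c = 0 and the odds ratio is 1.

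**Results.** Approximation first; in brackets, a large-sample logistic simulation with 1 case to 7 controls and no covariates or matching.

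| f | d (SD) | RR | q | As planned | mITT controls, unadjusted |
|---|---|---|---|---|---|
| any | 0 | 1 or 2 | – | 1.00 (1.00) | 1.00 (1.00) |
| 5% | −0.25 | 1 | 0.050 | exp(−0.0125) = 0.99 (0.99) | 1.00 (1.00) |
| 10% | −0.5 | 1 | 0.100 | exp(−0.050) = 0.95 (0.95) | 1.00 (1.00) |
| 10% | −1 | 1 | 0.100 | exp(−0.100) = 0.90 (0.90) | 1.00 (1.00) |
| 10% | −0.5 | 2 | 0.182 | exp(−0.091) = 0.91 (0.91) | exp(−0.041) = 0.96 (0.96) |
| 10% | −1 | 2 | 0.182 | exp(−0.182) = 0.83 (0.84) | exp(−0.082) = 0.92 (0.93) |
| 20% | −1 | 2 | 0.333 | exp(−0.333) = 0.72 (0.72) | exp(−0.133) = 0.88 (0.89) |

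Per-protocol cases with per-protocol controls gave about 1.00 in every setting.

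**Scale.** SE(log OR per SD) ≈ √(1/51 + 1/357) = 0.150, so a 95% interval spans a factor of exp(1.96 × 0.150) = 1.34 either way. At f = 10% and equal risk, the shift is 0.050/0.150 = 0.3 to 0.100/0.150 = 0.7 standard errors. With d = −1 SD and RR = 2 it is 0.182/0.150 = 1.2 standard errors. At f = 5%, d = −0.25 and RR = 1 it is under 0.1.

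**The case against.** **The SAP already plans the analysis that removes the mismatch.** This is true: the per-protocol-only run does so. But it is one of three sensitivity analyses, so the main estimate stays exposed.

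**The size rests on assumption.** This stands. Several exclusions, such as a staged procedure or malignancy found at surgery, have no evident link to titer before surgery. Late surgery is a weak example, since protocol section 1.2.4 reports responses sustained through Month 12. Cases after a non-index procedure are also unclear: SAP 5.1 admits any spinal surgery to mITT, while 5.5 and 5.6.2 bar subjects without the planned index surgery from immunogenicity analyses.

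**The calculation simplifies the design.** It uses one titer distribution, whereas the SAP fixes 5 vaccinated and 2 unvaccinated controls per case. Vaccination status is not in the covariate list; it appears only as a candidate interaction. A simulation assumed cases split equally by arm, vaccination raising titer by 2 SD, and titers 1 SD lower in non-per-protocol vaccinees (10%, equal risk). Without vaccination status in the model, the odds ratio per pooled SD was 0.70 as planned and 0.73 with either alternative. With it, the values were 0.93 and 1.00. So the mismatch is not the only influence on this model, and the null value of 1.00 for the alternatives presumes that vaccination status is adjusted for. The mismatch still adds to the error in both versions.

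**The work is exploratory and post-futility.** This is correct, and it limits the weight of the point.

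**Conclusion.** The concern holds in a limited form. The main Objective 1 model draws cases and controls from different populations, without a stated reason, and this can bias the odds ratio if per-protocol status is related to titer after adjustment. A plausible distortion under no true effect runs from negligible (about 0.98 to 0.99) through about 0.90 to 0.95 to about 0.84. The lowest value needs 10% non-per-protocol subjects, a 1 SD titer deficit and doubled infection risk together. All of these rest on assumed inputs, and most are smaller than one sampling standard error.

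A reader might infer that the reported association will be biased, or biased toward protection. The documents do not support that: they give no non-per-protocol share, no count of non-per-protocol cases and no titer difference, and with no titer difference there is no bias. A reader might also infer that mITT controls alone cure the problem. They do not if non-per-protocol status also raises infection risk: about 0.93 remained at 10%, 1 SD and doubled risk. The trial's efficacy conclusion is not touched.

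**What to change.** In SAP 8.1.3.5 and Table 26, take one of two routes.

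1. **Make the planned analysis of per-protocol cases with per-protocol controls the primary Objective 1 result**, and report the all-case model as the sensitivity analysis. This needs no new subjects or assays and works even if controls are already assayed. It drops the non-per-protocol cases and confines the conclusion to per-protocol subjects. At 10% non-per-protocol, about 5 of 51 cases go if risk is equal (51 × 0.100) and about 9 if it is doubled (51 × 0.182). If their controls go too, the standard error rises from 0.150 to √(1/46 + 1/322) = 0.158 or √(1/42 + 1/294) = 0.165.

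2. **If controls are not yet assayed, sample them from mITT subjects at the same site** without confirmed *S. aureus* infection, and include per-protocol status as a covariate kept out of the selection procedure. The number of controls and assays is unchanged, and all cases are kept.

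Either way, report the number of non-per-protocol cases so that readers can judge how much the choice matters.
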